**Effect of Chronic Exenatide Therapy on Beta Cell Function and Insulin Sensitivity in T2DM**

## **Study A.**

**Subjects:** 80 T2DM subjects (age = 18-70 years; BMI = 21-45 kg/m^2; male or female) according to the ADA criteria will participate in the study. Subjects must be drug naïve and/or on a stable dose (more than 3 months) of metformin and/or sulfonylurea and have HbA1c >7.0% and <10.5%. Subjects taking drugs known to affect glucose metabolism (other than metformin and sulfonylurea) will be excluded. Other than diabetes, subjects must be in good general health as determined by physical exam, medical history, blood chemistries, CBC, TSH, EKG and urinalysis. Only subjects whose body weight has been stable ( $\pm$  3 lbs) over the preceding three months and who do not participate in an excessively heavy exercise program will be included. Individuals with evidence of proliferative diabetic retinopathy, plasma creatinine >1.4 females or >1.5 males will be excluded. Diabetic subjects will be recruited from the South Texas Veterans Health Care System and Texas Diabetes Institute (TDI) in San Antonio (Deputy Director = [name]). TDI is the largest institute in the United States that provides comprehensive care for ~ 10,000 unduplicated T2DM patients. Therefore, we do not anticipate any problem in recruiting the required number of patients for this study.

**Study design:** After screening, eligible subjects will receive a measurement of endogenous glucose production (EGP) with a prime-continuous infusion of 3-H-glucose. The EGP measurement will be performed in the morning after a 10-12 hour overnight fast and will last 8.5 hours (from 6 AM to 2:30 PM). After a 3.5-hour tracer equilibration period, subjects (20 per group) will receive one of the following medications: (i) placebo; (ii) exenatide 5 ug subcutaneously; (iii) dapagliflozin (10 mg); and (iv) dapagliflozin 10 mg plus exenatide 5 ug (see flow diagram on page 11). Following the test medication at 9:30 AM, blood samples will be drawn every 10-20 minutes for an additional 5 hours and plasma glucose, insulin, C-peptide, glucagon concentrations and glucose specific activity will be measured. One-two weeks after the EGP measurement, participants will come back for the Double Tracer Oral Glucose Tolerance Test (DT-OGTT).

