**Data Analysis and Statistical Methods:** The **primary end point** of the study is the change in EGP during **Study A**. The difference in the rate of EGP during the last hour of the study (i.e. from 240-300 minutes) between drug-treatment and placebo-treatment studies represents the effect of drug treatment on EGP. The difference in EGP will be compared among the 3 drug treatments (exenatide, dapagliflozin, and exenatide plus dapagliflozin) with ANOVA. Post hoc testing will be performed with a Bonferroni correction for multiple

comparisons. The following primary comparison will be performed: (i) the change in EGP above baseline following dapagliflozin alone versus dapagliflozin/exenatide. The following secondary comparisons will be made: (i) the change in EGP above baseline following exenatide alone versus dapagliflozin/exenatide and (ii) the change in EGP above baseline following dapagliflozin alone, exenatide alone, and dapagliflozin/exenatide versus the change in EGP following placebo. Between group comparisons will be made with repeated measures ANOVA with time and treatment group as factors.

**Other secondary end points** will be: (i) the decrement in the fasting plasma glucose conc at the end of the study compared to baseline, (ii) change in plasma glucagon conc at the end of the study compared to baseline; and (iii) change in plasma insulin conc at the end of the study compared to baseline. Secondary end points will be compared using the same statistical methods described for the primary end point.

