**Anticipated Results and Data Interpretation.** Consistent with our published data (10), we anticipate that EGP will decrease progressively following placebo administration while, after an initial decline, EGP will increase progressively following dapagliflozin. We anticipate that plasma glucagon conc will increase and plasma insulin concentration will decrease following dapagliflozin administration. We anticipate that a single administration of exenatide will cause an increase in plasma insulin conc and a decrease in plasma glucagon conc compared to placebo. The increase in plasma insulin and decrease in plasma glucagon conc following exenatide administration will result in a greater decline in both EGP and fasting plasma glucose conc compared to placebo. Most importantly, we anticipate that the increase in plasma glucagon conc, the decrease in plasma insulin conc, and rise in EGP following dapagliflozin administration will be prevented, at least in part, if not totally, when exenatide is co-administered with dapagliflozin. Therefore, we anticipate an additive, even synergistic, decrease in plasma glucose conc and EGP following co-administration of dapagliflozin plus exenatide compared to either drug alone.

**Sample Size Calculation:** In our published results (10), the difference in the rate of basal EGP during the last hour of EGP measurement in dapagliflozin-treated and placebo-treated individuals was  $0.70 \pm 0.34$  (mean  $\pm$  SD). To detect a 50% decrease in the difference at alpha = 0.005 ( $=0.5/10$ ) (split alpha for up to 10 multiple comparisons and a Bonferroni correction) in exenatide plus dapagliflozin versus dapagliflozin alone, we computed that 17 subjects in each group provided 90% power. To ensure 17 completers assuming 15% lost to follow-up, we have set the sample size at 20 ( $=17/0.85$ ) in each group.

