### **Study C (see flow sheet below).**

Following completion of the OGTT (Visit 7), subjects will be started on Bydureon, 2 mg sc per week. Subjects will return of interim follow up visits at weeks 6, 8, 10, 13-14, (visits 8, 9,10, 11. During the weeks 16-18 (visit 12),subjects will have a repeat Double Tracer OGTT (visit 12) will be performed..

**Visits 8, 9, 10, and 11. Brief Follow Up Visits** for interim medical history and compliance with the Bydureon regimen.

**Visit 12: Double Tracer OGTT** will be performed as per **Visit 3**.

The treatment period could be extended based upon the circumstances (based upon the situation of COVID-19 pandemic) until the repeat studies are completed.

**Data Analysis:** In **Study B**, we anticipate that dapagliflozin and Byetta will produce similar reductions in HbA1c and that the combination of dapagliflozin plus Byetta will produce an additive/near-additive reduction in A1c. We anticipate that both dapagliflozin and Byetta monotherapy will produce significant weight loss and that the combination will produce an additive, even synergistic, effect on weight loss.

We anticipate that that the dapagliflozin-induced rise in EGP will persist after 1 month in T2DM patients receiving dapagliflozin monotherapy even though both beta cell function and peripheral insulin sensitivity improve. We expect that Byetta-treated T2DM patients will experience a reduction in both fasting and postprandial plasma glucose levels during the DT-OGTT, markedly enhanced beta cell function, improved peripheral tissue insulin sensitivity, and reduced fasting and postprandial plasma glucagon concentrations during the DT-OGTT. In T2DM patients receiving combined Byetta/dapagliflozin therapy, we hypothesize that exenatide will block the dapagliflozin-induced rise in glucagon secretion and overcome the dapagliflozin-induced decrease insulin secretion, resulting in a greater suppression of EGP. Because we anticipate that Byetta will offset the negative effects of dapagliflozin on EGP and on insulin and glucagon secretion, we expect that the decline in fasting and postprandial glucose concentrations during the DT-OGTT will be enhanced in T2DM subjects receiving combination Byetta/dapagliflozin therapy.

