**Sample Size Calculation:** In our published results (10), the difference in the rate of basal EGP during the last hour of EGP measurement in dapagliflozin-treated and placebo-treated individuals was  $0.70 \pm 0.34$  (mean  $\pm$ SD). To detect a 50% decrease in the difference at alpha = 0.167 ( $=0.5/3$ ) (split for 3 comparisons and a Bonferroni correction) in Byetta plus dapagliflozin versus dapagliflozin alone, we computed that 13 subjects in each group will provide 90% power.

**Data Analysis:** In **Study C**, we anticipate that dapagliflozin and Bydureon will produce similar reductions in HbA1c and that the combination of dapagliflozin plus Bydureon will produce an additive/near-additive reduction in A1c. We anticipate that both dapagliflozin and Bydureon monotherapy will produce significant weight loss and that the combination will produce an additive, even synergistic, effect on weight loss.

We anticipate that that the dapagliflozin-induced rise in EGP will persist after 4 months in T2DM patients receiving dapagliflozin monotherapy even though both beta cell function and peripheral insulin sensitivity improve. We expect that Bydureon-treated T2DM patients will experience a reduction in both fasting and postprandial plasma glucose levels during the OGTT, markedly enhanced beta cell function, improved peripheral tissue insulin sensitivity, and reduced fasting and postprandial plasma glucagon concentrations during the DT-OGTT. In T2DM patients receiving combined Bydureon-dapagliflozin therapy, we hypothesize that exenatide will block the dapagliflozin-induced rise in glucagon secretion and overcome the dapagliflozin-induced decrease insulin secretion, resulting in suppression of EGP. Because we anticipate that Bydureon will offset the negative effects of dapagliflozin on EGP and on insulin and glucagon secretion, we expect that the decline in fasting and postprandial glucose concentrations during the DT-OGTT will be enhanced in T2DM subjects receiving combination Bydureon/dapagliflozin therapy.

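### Studies B and C name no deciding outcome and split alpha over three comparisons only, although effects are expected on nine or more outcomes

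*Combined protocol and SAP*

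**What the plan says.** The Data Analysis and Statistical Methods paragraph under Study A is the only place that ranks outcomes. The primary end point "of the study is the change in EGP during" Study A, with one primary comparison (dapagliflozin versus dapagliflozin plus exenatide). The secondary comparisons and end points that follow also belong to Study A.

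For Studies B and C, the two Data Analysis paragraphs (both printed under the Study C heading) describe anticipated results. They name no primary outcome, no test and no testing order. Effects are expected on HbA1c, weight, EGP, fasting and postprandial glucose, and, for the exenatide products, "markedly enhanced beta cell function, improved peripheral tissue insulin sensitivity, and reduced fasting and postprandial plasma glucagon concentrations during the DT-OGTT". That is nine outcomes; insulin secretion, mentioned for the combination, would make ten.

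Each study nevertheless has its own sample size paragraph, based on one outcome and one contrast: basal EGP, combination versus dapagliflozin alone. Both read "To detect a 50% decrease in the difference at alpha = 0.167", shown as 0.5/3 and explained as "split for 3 comparisons and a Bonferroni correction". Both conclude "we computed that 13 subjects in each group will provide 90% power".

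The title of the document is "Effect of Chronic Exenatide Therapy on Beta Cell Function and Insulin Sensitivity in T2DM".

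**The concern.** A Bonferroni split tells the reader that the error rate of a study is under control. Here it covers three comparisons on one outcome. Nothing covers the step from one outcome to nine or more, and no text says which of them decides the study.

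The documents point in two directions. The sizing suggests EGP; the title suggests beta cell function and insulin sensitivity. Without a named outcome, a positive result for Study B or C could rest on whichever outcome and contrast came out significant, and the stated correction would not reveal how many were tried. The printed alpha adds to this, since three tests at 0.167 do not hold 5% even for one outcome.

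**Working it through.** **Inputs from the documents.** Reference difference 0.70, SD 0.34, 50% decrease, so delta = 0.35; alpha printed as 0.167 (0.5/3); power 90%; 13 per group; three arms continue (Study B text: placebo is not carried forward); 20 per arm at entry (study design figure).

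**Assumptions.** The three comparisons are the pairwise arm contrasts; tests are two-sided; every outcome is tested on every contrast; outcomes are equally correlated. The documents state none of these.

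**Step 1: the plan's own figure.** For two groups, n = 2 × (z₁₋α/₂ + z₀.₉₀)² × (SD/delta)².
- Alpha 0.5/3: 2 × (1.383 + 1.282)² × (0.34/0.35)² = 13.4, against 13 stated. Power at 13 is 88% to 89%. The printed alpha therefore roughly reproduces the figure.
- Alpha 0.05/3: 2 × (2.394 + 1.282)² × (0.34/0.35)² = 25.5, so 26 per group (27 by t test). Power at 13 is 53% (t test) to 59% (normal formula).
- A one-sample formula at 0.05/3 gives half of 25.5, or 12.75, which rounds up to 13.

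The figure of 13 therefore does not settle which alpha was meant. The Study A paragraph is a clue. Its alpha of 0.005, "split alpha for up to 10 multiple comparisons and a Bonferroni correction", is shown as 0.5/10, but 0.5/10 = 0.05 and 0.05/10 = 0.005. So 0.5 there is a misprint for 0.05, and 0.05/3 = 0.0167 is the likely intention in B and C.

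**Step 2: one outcome, three contrasts, no true effects.**
- At 0.0167: Bonferroni bound 3 × 0.0167 = 0.05; simulated for three arms of 13, about 0.04.
- At 0.167: bound 3 × 0.167 = 0.50; if independent, 1 − (1 − 0.1667)³ = 0.42; simulated, about 0.35.

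**Step 3: nine outcomes, three contrasts, 0.0167 per test.** There are 9 × 3 = 27 tests. If all were independent, 1 − (1 − 0.0167)²⁷ = 0.365. The contrasts share arms, so the simulation (three arms of 13, pairwise t tests) is more realistic:

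| Outcome correlation (assumed) | Chance of at least one false positive per study |
|---|---|
| 0 | 0.33 |
| 0.3 | 0.30 |
| 0.5 | 0.26 |
| 0.7 | 0.20 |
| 0.8 | 0.17 |
| 0.9 | 0.12 |

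Runs with 20 per arm agree to about 0.01 (0.34, 0.25 and 0.16 at correlation 0, 0.5 and 0.8). With insulin secretion as a tenth outcome, the values at 0, 0.5 and 0.9 are 0.36, 0.28 and 0.13.

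**Step 4: effect of one deciding contrast on power** (delta 0.35, SD 0.34, two-sided two-sample t test).

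| Per arm | Alpha 0.0167 | Alpha 0.05 |
|---|---|---|
| 13 | 53% | 71% |
| 20 | 77% | 89% |

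For 90% power at 0.05 the t test needs 21 per arm.

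**The case against.** The best defence is that the trial has one primary end point, in Study A, and that B and C are mechanistic follow-on phases for which control over every outcome is not customary. The sizing paragraphs already single out EGP, combination versus dapagliflozin, so only a label is missing. This stands in part: the gap is in the declaration, and the repair is correspondingly small. It does not remove the point, because B and C claim their own alpha and a Bonferroni correction, and sizing on an outcome does not make it the deciding one. Where the authors wanted a primary, in Study A, they named it.

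It is also fair that the 27 tests are a construction. The text lists anticipated results, several of them within one arm, and the three comparisons are never spelled out. The error rates show what happens if every outcome is tested on every contrast, which the plan neither schedules nor rules out.

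Three stronger readings are tempting but not supported:
- A single figure, such as 25% in place of 5%. It needs an outcome correlation near 0.5, which no section supplies, and 5% is not the printed starting level.
- A higher per-study rate because there are two time points. Studies B and C have one repeat double tracer oral glucose tolerance test (DT-OGTT) each, at day 28 and at weeks 16-18, so a second time point does not enter a per-study rate.
- A prediction that EGP and beta cell function will give opposite answers. The sentence on patients "receiving dapagliflozin monotherapy even though both beta cell function and peripheral insulin sensitivity improve" concerns the dapagliflozin arm alone. For the combination versus dapagliflozin, the documents predict no such conflict.

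**Conclusion.** The point holds. Studies B and C have their own sample size and alpha but no named deciding outcome, and the alpha is split over three comparisons while nine or more outcomes carry expected effects. If 0.0167 was meant, the chance of at least one false positive is about 12% to 33% per study, given nine outcomes each tested on three pairwise arm contrasts with correlation between 0.9 and 0. At the alpha as printed, one outcome alone gives about 35%. The direction does not depend on the correlation: every value in the range is more than twice 5%. Study A keeps its named primary end point and comparison, so this should be corrected but does not undermine the trial's primary result.

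**What to change.** In the Data Analysis and Sample Size Calculation paragraphs for Studies B and C:

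1. Name EGP, combination versus dapagliflozin alone, as the single deciding test in Study B (day 28), at two-sided 0.05. Test the same contrast in Study C (weeks 16-18) only if Study B is significant; otherwise label it secondary.
2. State the EGP time window on the DT-OGTT. The sizing EGP comes from the last hour of the separate EGP study, which B and C do not repeat; the DT-OGTT includes a 75 g glucose load at time zero.
3. Label all other B and C outcomes and arm contrasts, including beta cell function and insulin sensitivity, as exploratory, reported as estimates with 95% confidence intervals.
4. Correct the printed 0.167 and restate the power. With the plan's own delta and SD, a single contrast at 0.05 has 71% power at 13 per arm and 89% at 20; whether that SD applies to the chosen DT-OGTT window should be stated.
5. Leave the Study A alpha as it is.

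This takes a few sentences and no new data or patients. The cost is that claims on HbA1c, weight, beta cell function and insulin sensitivity in B and C would not be confirmatory, although the last two are in the title.

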## STUDY DESIGN

[figure not shown]
Placebo  
(n=20)

Byetta  
(n=20)

Dapagliflozin  
(n=20)

Byetta/Dapagliflozin  
(n=20)

### 3-H-glucose turnover study/DT-OGTT/A1c x 2

### COMPARISONS during initial 3-H-glucose turnover study

Byetta/Dapa vs Dapa  
vs Byetta  
vs Placebo

Dapa vs Byetta  
vs Placebo

Byetta vs Placebo

### 3-H-GLUCOSE TURNOVER STUDY

Time (min)	Glucose (0.5 ml)	Insulin (1.5 ml)	C-peptide (1.5 ml)	Glucagon (1.5 ml)	3-H-glucose (2 ml)
-210	X				
Start 3-  H-glucose AT -210					
-60	X	X	X	X	X
-50	X	X	X	X	X
-45	X				X
-40	X	X	X	X	X
-35	X	X			X
-30	X	X	X	X	X
Ingest dapagliflozin at -30 minutes					
-20	X	X	X	X	X
-10	X	X	X	X	X
0	X	X	X	X	X
Inject Byetta at time zero					
15	X	X	X	X	X
30	X	X	X	X	X
45	X	X	X	X	X
60	X	X	X	X	X
75	X				X
90	X	X	X	X	X
105	X				X
120	X	X	X	X	X
135	X				X
150	X	X	X	X	X
165	X				X
180	X	X	X	X	X
200	X				X
220	X	X	X	X	X
240	X				X
260	X	X	X	X	X
280	X	X	X	X	X

285	X				X
290	X				X
295	X				X
300	X	X	X	X	X
Number	30	20	20	19	30
Volume (ml)	15	30	30	29	60

Total Volume = 164 ml

### DOUBLE TRACER ORAL GLUCOSE TOLERANCE TEST (DT-OGTT)

Time (min)	Glucose (0.5 ml)	Insulin (1.5 ml)	C-peptide (1.5 ml)	Glucagon (1.5 ml)	3-H-glucose (2 ml)	1-C-glucose (4 ml)
----------------------	------------------------------------	------------------------------------	--------------------------------------	-------------------------------------	--	---

-180 X

Start tritiated glucose at -180 minutes

-60 X X X X X

-50 X X X X X

-45 X X X X X X

-40 X X X X X

-35 X X X X X

-30 X X X X X X

Ingest dapagliflozin at -30 minutes

-20 X X X X X

-10 X X X X X

0 X X X X X X

Inject Byetta at time zero; ingest 75 gm glucose with C-glucose at time zero

15 X X X X X X

30 X X X X X X

45 X X X X X X

60 X X X X X X

75 X X X X X X

90 X X X X X X

105 X X X X X X

120 X X X X X X

150	X	X	X	X	X	X
180	X	X	X	X	X	X
210	X	X	X	X	X	X
240	X	X	X	X	X	X
270	X	X	X	X	X	X
280	X	X	X	X	X	X
290	X	X	X	X	X	X
300	X	X	X	X	X	X
Number	24	22	22	20	25	17
Volume (ml)	12	33	33	30	50	68

Total blood volume = 226 ml

#### Exclusion Criteria

1. Presence of significant systemic disease, heart problems including congestive heart failure, unstable angina or acute myocardial infarction, current infectious liver disease, acute stroke or transient ischemic attacks, history of pancreatitis, urosepsis and pyelonephritis, genital mycotic infections, or Type 1 diabetes mellitus
2. Any hepatic diseases in the past (infectious liver disease, viral hepatitis, toxic hepatic damage, jaundice of unknown etiology) or severe hepatic insufficiency and/or significant abnormal liver function tests defined as aspartate aminotransferase (AST) >3x upper limit of normal (ULN) and/or alanine aminotransferase (ALT) >3x ULN
3. Renal impairment (e.g., serum creatinine levels  $\geq 1.4$  mg/dL for women or  $\geq 1.5$  mg/dL for men, or eGFR  $< 60$  mL/min/1.73 m^2) or history of unstable or rapidly progressing renal disease or end stage renal disease.
4. Uncontrolled thyroid disease, Cushing's syndrome, congenital adrenal hyperplasia or hyperprolactinemia
5. Significantly elevated triglyceride levels (fasting triglyceride  $> 400$  mg/dL), uncontrolled increased LDL-C
6. Untreated or poorly controlled hypertension (sitting blood pressure  $> 160/95$  mm Hg)
7. Use of anti-obesity drugs or weight loss medications (prescription or OTC) and medications known to exacerbate glucose tolerance (such as isotretinoin, GnRH agonists, glucocorticoids, anabolic steroids, C-19 progestins) stopped for at least 8 weeks. Use of anti-androgens that act peripherally to reduce hirsutism such as 5-alpha reductase inhibitors (finasteride, spironolactone, flutamide) stopped for at least 4 weeks

8. Prior history of a malignant disease requiring chemotherapy, prior history of bladder cancer regardless treatment
9. Patients at risk for volume depletion due to co-existing conditions or concomitant medications, such as loop diuretics should have careful monitoring of their volume status
10. History of unexplained microscopic or gross hematuria, or microscopic hematuria at visit 1, confirmed by a follow-up sample at next scheduled visit.
11. Presence of hypersensitivity to dapagliflozin or other SGLT2 inhibitors (e.g. anaphylaxis, angioedema, exfoliative skin conditions)
12. Known hypersensitivity or contraindications to use GLP1 receptor agonists (exenatide, liraglutide)
13. Use of , thiazolidinediones, GLP-1 receptor agonists, DPP-4 inhibitors, SGLT2 inhibitors stopped for at least 8 weeks.
14. Eating disorders (anorexia, bulimia) or gastrointestinal disorders
15. Suspected pregnancy (documented negative serum  $\beta$ -hCG test), desiring pregnancy in next 6 months, breastfeeding, or known pregnancy in last 2 months
16. Active history of illicit substance abuse or significant intake of alcohol
17. Having a history of bariatric surgery
18. Patient not willing to use two barrier method contraception during study period (unless sterilized or have an IUD)
19. Debilitating uncontrolled psychiatric disorder such as psychosis or neurological condition that might confound outcome variables
20. Inability or refusal to comply with protocol
21. Current participation or participation in an experimental drug study in previous three months

## **Safety**

### **Definition of adverse events**

An adverse event is the development of an undesirable medical condition or the deterioration of a pre-existing medical condition following or during exposure to a pharmaceutical product, whether or not considered causally related to the product.

The term AE is used to include both serious and non-serious AEs.

